1 BACKGROUND

Musculoskeletal pain is extremely common and the leading cause of physical disability. Opioids are potent analgesics that may be used to treat musculoskeletal pain, such as knee osteoarthritis (1). Several opioid analgesics are available and are increasingly used for the treatment of pain because, in contrast to NSAIDs, opioids do not produce gastrointestinal bleeding or renal problems. This makes opioids an attractive option.

Disequilibrium and gait disturbance are the most common causes of falls, which are becoming a serious social problem for the increasing geriatric population. Important side effects to opioid usage are dizziness and gait ataxia (2) which may cause loss of limb coordination and unsteady gait that predispose to falls. In the elderly, fall related fractures are considered a serious risk factor for increased disability and approximately 20% die within the first 3-6 months after a hip fracture (3). Because balance deficits are not uncommon among musculoskeletal pain patients (3;4), gait ataxia and increased risk of falling is a particular safety issue in knee osteoarthritis. However, no studies have assessed opioid induced gait ataxia in humans.

While the analgesic effects of opioids are well known, empirical clinical evidence suggest that there are differences in the dizziness and gait ataxia profiles of the different opioid types. However, this has not been investigated scientifically under controlled conditions, in part due to lack of sensitive methods to discriminate between levels of ataxia. Three-dimensional biomechanical movement analysis is a sensitive method to assess gait ataxia, as excess variability in gait parameters, however it is unknown if this method can discriminate between the gait ataxia induced by different opioid types.

This study is designed as an experimental, randomized, double-blind, cross-over study of the differences in pharmacologically induced gait ataxia between two different opioid formulations and placebo in healthy volunteers and patients with knee osteoarthritis.

1.1 Investigational Agents

This study includes 2 investigational agents, *Tapentadol* and *Tramadolhydrochlorid*, and 1 inert placebo.

Tapentadol is a centrally acting analgesic acting as a μ -opioid receptor agonist and as a norepinephrine reuptake inhibitor (5). The analgesic effect of Tapentadol is direct without conversion to a pharmacologically active metabolite.

Tramadolhydrochlorid is a centrally acting analgesic acting as a μ -opioid receptor agonist, induction of serotonin release, and inhibition of norepinephrine reuptake (6;7). The analgesic effect of Tramadolhydrochlorid is almost exclusively mediated through the pharmacologically active metabolite O-desmethyltramadol, a potent μ -opioid receptor agonist.

1.2 Overview of relevant data

There are no studies evaluating the effects of opioid induced gait ataxia. The vast majority of knowledge is from clinical studies of safety, in which frequencies of side effects are reported. In a recent meta-analysis on efficacy and safety of opioids in osteoarthritis self-reported dizziness were among the most common side effects (2). One study has shown a significant relationship between cognitive and motor function decrements and plasma opioid concentration (8). Another study has shown that there seems to be an inhibitory effect of opioids on motor neurons (9).

1.3 Risk/Benefits

The analgesic effects of opioids are well known, and opioids are among the world's oldest known drugs for pain relief.

The most common side effects in patients taking opioids for pain relief include nausea, constipation, dizziness, somnolence, and vomiting. Infrequent adverse reactions in patients taking opioids for pain relief include: dose-related respiratory depression, confusion, hallucinations, delirium, urticaria, hypothermia, bradycardia/tachycardia, orthostatic hypotension, dizziness, headache, urinary retention, ureteric or biliary spasm, muscle rigidity, myoclonus (with high doses), and flushing. Risk of opioid dependencies with one opioid dosage (Tapentadol and Tramadolhydrochorid) is estimated not to exist.

1.4 Dose Rationale

This study includes 2 investigational agents; *Tapentadol* and *Tramadolhydrochlorid*, and 1 inert placebo. Both active agents are given as extended release formulations as tablets. *Tapentadol* is administered in a 50 mg formulation (Palexia Depot, Grünenthal). *Tramadolhydrochlorid* is administered in a 100 mg formulation (Mandolgin Retard, Sandoz).

These dosages are chosen because they are considered equianalgesic.

All participants are given both investigational agents and the inert placebo. One tablet is administered per study visit. The order of tablets is decided through randomization. The study visits are separated by at least 7 days.

1.5 Population

When investigating the potential differences in dizziness and gait ataxia between different opioid types in a population that has pain it is difficult to discern the effects of pain relief from central nervous system side effects, because pain relief in itself may affect gait variability in a way that may mask gait ataxia. Therefore, a healthy control group without pain is included because dizziness and gait ataxia in this population with confidence can be attributed to side effects on motor function in the central nervous system (gait ataxia). This information can be used to distinguish between increased gait variability caused by pain relief from centrally derived gait ataxia in the patient population.

2 STUDY OBJECTIVES

The purpose of this study is to investigate if differences in gait ataxia induced by two different single-dose opioid formulations and inert placebo can be detected by 3D gait analysis in healthy volunteers and knee osteoarthritis patients.

[figure not shown]
3 STUDY DESIGN

The study is designed as an experimental single center, double-blind treatment, cross-over study with placebo, Palexia Depot, and Mandolgin Retard, with a minimum of 7days washout periods. All participants are required to attend to 3 full day examinations at The Clinical Motor Function Laboratory at The Parker Institute, Department of Rheumatology, Copenhagen University Hospital - Frederiksberg.

3.1 Study Design/Type

The study is designed as an experimental single center, double-blind treatment, cross-over study with inert *placebo*, *Tapentadol* (Palexia Depot), and *Tramadolhydrochlorid* (Mandolgin Retard), with a minimum of 7days wash-out periods.

At day 1 (Visit 1), baseline measurements are carried out before tablet administration. Immediately after baseline measurements one tablet is administered, and hourly measurements are performed for 6 hours. Subsequently all participants enter a minimum 7 day washout period, after which they return to the facility to repeat the procedures at Visit 2 (day 8+) and Visit 3 (day 15+). The order of treatments will be randomized (1:1:1). The design is illustrated below:

3.2 Primary Study Endpoints/Secondary Endpoints

Primary outcome:

- Change from the post-washout baseline in gait variability over time Secondary outcomes:
 - Change from the post-washout baseline in autonomous nerve system assessments over time
 - Change from the post-washout baseline in plasma concentrations of opioid metabolites over time
 - Change from the post-washout baseline in participant assessment of dizziness, nausea, and other adverse effects over time
 - Change from the post-washout baseline in knee pain (patients only) using 100 mm
 Visual Analogue Scale (VAS) over time

3.3 Randomization

The biostatistician is responsible for preparation of the randomized group allocation list before initiation of the study. Two randomization lists are developed; one for the OA patients and one for the healthy volunteers. The same randomization technique is used for both lists:

Each participant is randomized to experimental group ABC, ACB, BCA, BAC, CBA, or CAB. ABC, ACB, BCA, BAC, CBA, or CAB denotes the order of the investigational products and placebo.

Generation of the code defining the actual denotation of A, B, and C is pending, but to illustrate the allocation generation, A could denote *Tramadolhydrochlorid*, B could denote *Tapentadol*, and C could denote *Placebo*.

In such allocation code, ABC denotes *Tramadolhydrochlorid* at the first visit, *Tapentadol* at the second visit, and *Placebo* at the third visit. ACB denotes *Tramadolhydrochlorid* at the first visit, *Placebo* at the second visit, and *Tapentadol* at the third visit. BCA denotes *Tapentadol* at the first visit, *Placebo* at the second visit, and *Tramadolhydrochlorid* at the third visit. BAC denotes *Tapentadol* at the first visit, *Tramadolhydrochlorid* at the second visit, and *Placebo* at the third visit. CBA denotes *Placebo* at the first visit, *Tapentadol* at the second visit, and *Tramadolhydrochlorid* at the third visit. CAB denotes *Placebo* at the first visit, *Tramadolhydrochlorid* at the second visit, and *Tapentadol* at the third visit.

The randomization will be 1:1:1 meaning that 4 participants (2 healthy volunteers and 2 patients) are randomly assigned to each order of agents. To account for drop-outs during the study, the randomization list will have 20 randomizations for both OA patients and healthy controls (yielding a total of 40 randomizations).

A coded randomization list will be available to the clinical staff administering the investigational products.

After obtaining signed informed consent form the participant, baseline measurements will be completed, and the clinical staff will administer the experimental product according to the coded randomization list.

Participants, scientific, clinical technical and assistive staff and other persons directly involved in clinical and preclinical examinations, measurements, and data analyses will be blinded to the group allocation.

Information that potentially can unblind study staff and/or participants will not be shared and will be stored under lock and with limited access, until the database of the study is locked.

3.4 Maintenance of the randomization

Prior to the study initiation, two folders (one for the healthy volunteers and one for the knee OA patients) each containing 20 envelopes are created. Each envelope will contain a piece of paper with the randomization code written on it representing the order of tablet administration but in a coded form (e.g. "123", "132", "231", "213", "312", and "321", corresponding to the order of products A, B, and C (see 3.3)). The order of the envelope content matches the randomization list. It is ensured that the envelopes are closed and opaque. The envelopes are numbered consecutively from 1-20 and placed in the folder according to the number (no. 1 in front – no. 20 in the back). The envelope numbers match the randomization numbers. The folders are stored in a locked locker in the clinical motor unction laboratory. Duplicates of the randomization list and envelopes are stored under lock in the research administration of the Parker Institute.

When a participant has completed the baseline assessments at Day 1, the participant is randomized. An envelope is drawn from the folder, starting from the front envelope. On the

front of the envelope, the participant's name, date of birth, screening number, and present date is written.

The investigator can immediately and any time request unblinding due to participant safety. Unblinding by the investigator is done by contacting the research administration of the Parker Institute and requesting a given participant's envelope to be opened in order to reveal the order of agent administration. Once unblinded, a participant cannot continue in the study.

The entire group allocation can be unblinded in the case of suspected unexpected adverse events related to the study.

3.5 Study Treatment

Tapentadol is administered as a single dose in a 50 mg formulation (Palexia Depot, Grünenthal). Tramadolhydrochlorid slow release is administered as a single dose in a 100 mg formulation (Mandolgin Retard, Sandoz). Inert placebo is administered as inert calcium tablets.

The tablets will be encapsulated to mask the tablets. The encapsulation will be performed at *Sygehusapotek Fyn, Odense Universitetshospital* according to GMP (Good Manufacturing Practice).

The tablets will be packed in triplets with one of each investigational product and one placebo. Each tablet will be packed in a small duma. On each duma, the number "1", "2" or "3" will be printed, to define the order of tablet administration. There will be an equal amount of each investigational product labeled "1", "2", and "3". A triplet of small dumas including one of each investigational products and one placebo will be packed together in a sealed labeled plastic container.

The content of each plastic container corresponds to the randomization list such that the plastic container allocated for a participant randomized to "123" will have product A in the duma labeled "1" to be administered at the first visit, product B in the duma labeled "2" to be administered at the second visit, and product C in the duma labeled "3" to be administered at the third visit. A participant randomized to "132" will have product A in the duma labeled "1" to be administered at the first visit, product C in the duma labeled "2" to be administered at the second visit, and product B in the duma labeled "3" to be administered at the third visit. A participant randomized to "231" will have product B in the duma labeled "1" to be administered at the first visit, product C in the duma labeled "2" to be administered at the second visit, and product A in the duma labeled "3" to be administered at the third visit. A participant randomized to "213" will have product B in the duma labeled "1" to be administered at the first visit, product A in the duma labeled "2" to be administered at the second visit, and product C in the duma labeled "3" to be administered at the third visit. A participant randomized to "312" will have product C in the duma labeled "1" to be administered at the first visit, product A in the duma labeled "2" to be administered at the second visit, and product B in the duma labeled "3" to be administered at the third visit. A participant randomized to "321" will have product C in the duma labeled "1" to be administered at the first visit, product B in the duma labeled "2" to

be administered at the second visit, and product A in the duma labeled "3" to be administered at the third visit.

3.6 Duration

The study is designed as an experimental cross-over study with a minimum 7 days washout period. Thus, the participants are expected to participate in the study for at least 15 days, with three days of clinical assessments (Visit 1, 2 & 3).

3.7 Discontinuation

3.7.1 Causes for Individual Subject Discontinuation

Participants may discontinue the study at any time by withdrawal of informed consent. Sponsor and investigator may discontinue a participant. The reason for discontinuation will be recorded on the CRF. Criteria for individual subject discontinuation by the sponsor or investigator include, but are not limited to:

- Any medical condition, including an Adverse Event, that, in the opinion of the Investigator, may jeopardize the subject's safety if he or she continues in the study
- Subject noncompliance with study schedule or procedures

3.7.2 Study discontinuation

Sponsor has the right to terminate this study at any time. Reasons may include the following:

- The incidence or severity of events that compromise the safety of the participants or pose a health risk
- Unsatisfactory subject enrollment

3.8 Product Accountability

The investigator and study personnel will be responsible for accounting for investigational agents (distribution, storage, and records) and following the guidelines for good clinical practice and national regulations.

4 SELECTION AND WITHDRAWAL OF SUBJECTS

4.1 Recruitment

Healthy volunteers are recruited via advertisements in local newspapers. Patients with knee osteoarthritis are recruited from the Osteoarthritis outpatients clinic at Copenhagen University Hospital Frederiksberg.

4.2 Inclusion Criteria

Healthy subjects:

- In general good health, in the opinion of the Investigator, based on medical history and physical examination.
- Ability to comprehend and a willingness to provide written informed consent
- Age between 50 and 75 years
- No opioid usage 3 months prior to the study
- No musculoskeletal pain requiring medical attention during the previous 3 months
- Willing and able to complete study visits and procedures

CONFIDENTIAL

10

- Willing to hold activity, exercise level, and concurrent treatments/therapies generally consistent during the study
- A body mass index (BMI) of ≤30

Patients with knee osteoarthritis

- Diagnosis of knee OA
- Ability to comprehend and a willingness to provide written informed consent
- Age between 50 and 75 years
- No opioid usage 3 months prior to the study
- Knee pain of at least 40 mm on a 0-100 mm visual analog scale (without analgesics) representing the average pain intensity during the previous week
- Willing to discontinue all pain medications 24 hours before and during examination visits
- Willing and able to complete study visits and procedures
- Willing to hold activity, exercise level, and concurrent treatments/therapies generally consistent during the study
- In general good health, in the opinion of the Investigator, based on medical history and physical examination.
- A body mass index (BMI) of ≤30

4.3 Exclusion Criteria

The same exclusion criteria apply for both healthy subjects and patients with knee osteoarthritis:

- Clinical signs of gait ataxia assessed by clinical neurological examination
- Independent or unsteady walking (i.e. dependence on walking device or stumbling gait)
- Counter indications to either of the investigational products (see Summaries of product characteristics; Appendix A and B), including but not restricted to:
 - Allergy towards one or more of the investigational products or their excipient(s).
 - Significant respiratory depression
 - Current or serious asthma
 - o Hypercapnia
 - Suspected or diagnosed paralytic ileus
 - Acute intoxication by alcohol, hypnotica, centrally acting analgesics, psychopharmaca or other pharmaceuticals.
 - o Renal dysfuntion
 - Hepatic dysfunction
 - o Diseases of the biliary tract
 - Acute pancreatitis
 - o Usage of monoamine oxidase inhibitors within the last 14 days
 - Galactose intolerance
 - Lactase deficiency
 - o Glucose/galactose malabsorption
 - Epilepsy
- Previous usage of opioids without pain reliving effect.

- Patients who have a documented history of an allergic reaction or a clinically significant intolerance to opioids
- Malignant pain
- Excessive joint laxity in the lower extremities indicative of functional ligamentous deficiency.
- Dependency of walking aid (stick, cane, roller etc.).
- Positive Clock Drawing Test
- Abuse of alcohol, medicine and narcotics within past 5 years.
- History of symptoms of autoimmune disorders
- Diabetes
- Pregnancy or breast feeding
- History, diagnosis, or signs and symptoms of clinically significant neurological disease
- History, diagnosis, signs or symptoms of any clinically significant psychiatric disorder

4.4 Subject Withdrawal and Replacement

In case of events during the clinical visits and measurements that preclude complete records, subjects are invited to re-enter the study at a later time. In such case the participant will be re-randomized.

4.5 Concomitant medication and therapies

Between visits Acetaminophen/Paracetamol (500 mg) to a maximum of 8 tablets per day is allowed. Participants must not take this medication for at least 24 hours before any assessment visit.

Concomitant non-pharmacological therapies (e.g. physiotherapy, acupuncture etc.) are allowed, but not for at least 24 hours before any assessment visit.

Concomitant pharmacological therapies for other conditions than musculoskeletal pain are allowed.

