7.3 Subject Population(s) for Analysis

The primary analyses will be based on the per-protocol (PP) population, defined as subjects that have completed the entire study.

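### Section 4.5 lets drugs for non-musculoskeletal conditions be taken with no pre-visit stop, so as-needed sedatives (and, in healthy volunteers, as-needed opioids) are not expressly barred before Visit 2 or 3

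*Protocol*

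**What the plan says.** Protocol section 4.5 contains three rules.

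- Paracetamol is permitted between visits, but "Participants must not take this medication for at least 24 hours before any assessment visit".
- Non-drug therapies such as physiotherapy "are allowed, but not for at least 24 hours before any assessment visit".
- For other drugs: "Concomitant pharmacological therapies for other conditions than musculoskeletal pain are allowed". This rule has no time limit and no exception.

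Other sections also restrict drug use.

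- Section 4.2, both groups: "No opioid usage 3 months prior to the study", and concurrent treatments are to be kept broadly stable.
- Section 4.2, patients with knee osteoarthritis only: "Willing to discontinue all pain medications 24 hours before and during examination visits". The healthy list has no matching item.
- Section 4.3, both groups: exclusion for contraindications to the study products, among them recent MAO inhibitor use and "Acute intoxication by alcohol, hypnotica, centrally acting analgesics, psychopharmaca or other pharmaceuticals", and for relevant neurological or psychiatric illness.
- Section 7.3: "The primary analyses will be based on the per-protocol (PP) population, defined as subjects that have completed the entire study".

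**The concern.** The primary outcome is step-to-step gait variability, read as drug-induced ataxia, and self-reported dizziness is a secondary outcome. A hypnotic, a sedating antihistamine or an opioid cough or headache product can plausibly affect both. As worded, the protocol stops paracetamol and physiotherapy before a visit but sets no stop for drugs of that kind.

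A drug taken in the same way at all three visits largely cancels in a cross-over. A tablet taken before one visit only does not. If it was taken the night before and wears off during the 6 hours of measurement, part of its effect enters the change from that visit's baseline.

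There is also a safety side. Participants aged 50 to 75 receive an opioid at two of three visits and walk repeatedly after dosing. The permission in 4.5 does not stop a sedative from being present at the same time.

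This is not a detail to be left to a statistical analysis plan. It is a stated permission about what participants may take, and an analysis plan cannot restrict that.

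**Working it through.** **Step 1: does another section close the gap?**

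| Provision | What it covers | What it leaves open |
|---|---|---|
| Opioid criterion, 4.2 | Both groups, the 3 months before the study | Use after enrolment |
| Stop of all pain medications, 4.2 | Patients, 24 hours before and during visits | Healthy volunteers, for whom 4.5 stops only paracetamol; sedatives in both groups |
| Stable treatments, 4.2 | Regular treatment in both groups | An occasional as-needed dose |
| Intoxication exclusion, 4.3 | Acute intoxication at selection | Ordinary doses |
| MAO inhibitor and disease exclusions, 4.3 | Many regular users of centrally acting drugs | As-needed use by people without such disease |
| Per-protocol set, 7.3 | Defined by completion | Does not separate visits with such a drug from those without |

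What remains is as-needed use after enrolment, shortly before Visit 2 or 3.

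**Step 2: reproduce the planned power.** Section 7.2 gives n = 24, difference 0.03, level 0.05 and power 80.4%. It states neither the SD nor the test. A two-sided paired t-test with SD 0.05 for the within-person difference has noncentrality (0.03/0.05) × √24 = 2.94 and power 80.37%, which matches. The SD is therefore back-solved and is an assumption.

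**Step 3: add the noise.** There are 24 × 3 = 72 visits. Let j of them be affected, independently with p = j/72, and let the other drug shift that visit's change score by e. As a simplification, the affected visits are spread over all 72. For a comparison of two drugs,

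SD = √(0.05² + 2p(1−p)e²).

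The documents give neither j nor e. Assumed values are j = 3, 6 or 9 and e = 0.015 (half the detectable difference), 0.03 (the detectable difference in 7.2) or 0.05 (the dual-task increase in 7.2).

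Example with j = 9 and e = 0.05: p = 0.125, so SD = √(0.0025 + 2 × 0.125 × 0.875 × 0.0025) = 0.0552 and power is 72.2%.

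| e | j = 3 | j = 6 | j = 9 |
|---|---|---|---|
| 0.015 | 80.1% | 79.8% | 79.6% |
| 0.03 | 79.3% | 78.2% | 77.3% |
| 0.05 | 77.3% | 74.6% | 72.2% |

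**Step 4: the same random effect seen as chance imbalance.** If j visits are drawn at random from 72 (24 per drug), two given drugs differ by 2 or more affected visits with probability 29%, 44% and 52% for j = 3, 6 and 9 (exact hypergeometric). A difference of 2 shifts the contrast by (2/24) × e, which is 0.00125, 0.0025 or 0.0042. Against the implied standard error of 0.05/√24 = 0.0102, that is about 0.12, 0.24 or 0.41 standard errors. Steps 3 and 4 describe one effect and should not be added together.

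**Step 5: walking load.** Section 5.1 asks for 25 walks of 10 m. Section 3.1 has a baseline and six hourly measurements, so 25 × 7 = 175 walks per visit.

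**The case against.** A reader might infer from 4.5 that the protocol allows every drug, opioids included. That is true only of the one sentence read alone. Sections 4.2 and 4.3 bar prior opioid use and several drugs and diseases, and patients must stop all pain medications, which covers an opioid taken for headache. The product summaries cited in 4.3 are not shown and may restrict sedatives further. This objection stands and confines the point to as-needed use after enrolment.

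A reader might also see a contradiction with section 1.5, which says of healthy volunteers that "dizziness and gait ataxia in this population with confidence can be attributed to side effects on motor function in the central nervous system". The contrast there is with patients whose gait may change through pain relief. It makes no claim about co-medication, and the 24-hour stops in 4.5 fit a concern with pain relief. So there is no internal contradiction. The sentence does show that a clean reading of central effects in volunteers matters to the design.

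The routes to harm are also limited. Visits are supervised full days, so a tablet taken after hour 0 is unlikely to go unnoticed. The model in 7.1 includes the daily baseline as a covariate, which partly adjusts for a baseline raised by a tablet from the night before. Up to 9 of 72 visits (12.5%) is high for a screened sample, and an effect of 0.03 or 0.05 is generous when only the part that wears off enters the change score. With e = 0.015 the loss of power is under 1 point. These arguments reduce the size but do not supply the missing rule.

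**Conclusion.** The point holds in a narrow form. Section 4.5 places no pre-visit restriction on drugs for non-musculoskeletal conditions, and the stop of all pain medications is listed for patients only. No provision shown expressly bars as-needed sedating drugs in either group, or as-needed non-study opioids and other non-paracetamol analgesics in healthy volunteers, shortly before Visit 2 or 3.

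A stronger reading would be that the drug comparison is biased. The documents do not support that: treatment order is randomised and staff and participants are blinded, so stray use falls on the drugs by chance. The effect is noise, and probably small. Power falls from 80.4% to between 80.1% and 72.2% over the assumed range, with the lower end needing both the highest frequency and the largest effect. All of this rests on an assumed SD of 0.05 and on assumed values of j and e.

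The safety concern does not depend on those figures: a sedative could be combined with a study opioid on a day with 175 walks. With so cheap a remedy, the change is worth making, although the gap does not threaten the trial's validity.

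**What to change.** Add to section 4.5, for both groups:

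1. No opioid other than the study drugs is taken until after Visit 3.
2. The stop of all pain medications, from 24 hours before a visit and during it, applies to healthy volunteers as well as patients.
3. As-needed sedating drugs (hypnotics, benzodiazepines, sedating antihistamines) are not taken from 24 hours before a visit until its last measurement. If one was taken, the visit is postponed.
4. Regular drugs for other conditions continue at an unchanged dose.

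The cost is a few sentences and an occasional postponed visit. The design can absorb this because the 7-day washout is a minimum. No run-in or extra visit is needed, and no regular treatment is stopped.
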